5.4 Study Treatment Dose Modifications, Interruptions, and Discontinuation

The following should be taken into consideration in decisions regarding management for treatment-related side effects: cabozantinib and IO agents have class-specific safety profiles based on their mechanisms of action but may also cause AEs that overlap. In the case of AEs clearly attributed to cabozantinib or the IO agent, independent dose modification for either agent is allowed.

- Examples of VEGFR TKI associated AEs caused by cabozantinib are hypertension and hand-foot syndrome.
- Examples of irAEs caused by IO agents are pneumonitis and endocrinopathies.
- Examples of overlapping AEs are diarrhea and elevations in liver function tests.

As a general approach all AEs should be managed with supportive care including both pharmacological and non-pharmacological treatments according to consensus management guidelines at the earliest signs of toxicity considered related to study treatment.

Study treatment may be continued for mild AEs if appropriate supportive care has been initiated to ameliorate symptoms. Should this be ineffective and toxicities become unacceptable, dose modifications of study treatment should be considered to prevent worsening of toxicity. Moderate to severe AEs usually require dose modifications including dose reductions and/or interruptions.

Dose interruptions of cabozantinib or IO agents for AEs may occur independent of the other agent at the discretion of the Investigator. If all study treatment is interrupted for more than 12 weeks, treatment should be discontinued unless approved by the Principal Investigator.

5.4.1 Management of AEs Associated with Cabozantinib

The following should be taken into consideration in decisions regarding dose modifications (reductions or interruption):

- As a general approach all AEs should be managed with supportive care at the earliest signs of toxicity considered related to the study treatment. Should this be ineffective, dose interruptions and/or reductions should be considered to prevent worsening of toxicity.
- The assigned starting dose for cabozantinib is 40 mg/day. Two dose reduction levels of cabozantinib are permitted (see "Dose Reductions of Cabozantinib" table).
- Dose modification criteria for cabozantinib are shown in the "Dose Reductions of Cabozantinib" table. Dose interruptions and/or reductions should be implemented for unacceptable toxicity.
 Doses may be modified at any time while a subject is on treatment.
- Dose reductions or interruptions may also occur in the setting of lower grade toxicity than
 defined in the "Dose Modifications of Cabozantinib for Treatment-Related AEs" table, if the
 Investigator feels it is in the interest of a subject's safety and will optimize drug tolerability.
- Interruption of cabozantinib treatment for cabozantinib-related AEs may occur at any time per Investigator discretion. If treatment is interrupted due to related AEs for more than 12 weeks, cabozantinib should be discontinued unless there is unequivocal evidence that the subject is

- benefitting. In this situation, a subject may be able to restart therapy with a dose reduction upon resolution of the toxicity, with approval from the Principal Investigator.
- Dose interruptions for reason(s) other than related AEs (e.g., surgical procedures) can be longer than 12 weeks per the discretion of the Investigator.
- Guidelines for the management of specific AEs of cabozantinib such as GI disorders, non-GI
 fistula formation, hemorrhage, thromboembolic events, hypertension, stomatitis and mucositis,
 skin disorders, osteonecrosis, proteinuria, nervous system disorders, infections and infestations,
 blood system disorders, fatigue, weight loss, QTc prolongation, electrolyte disorders, endocrine
 disorders, respiratory disorders and hepatic adverse events begin in Section 5.4.1.2.

Dose Reductions of Cabozantinib

Assigned Dose	First Dose Level Reduction	Second Dose Level Reduction	Third Dose Level Reduction
40 mg daily (qd)	20 mg daily (qd)	20 mg every other day (qod)	No dose reduction permitted
Cabozantinib will be discontinued if a dose of 20-mg cabozantinib every other day (minimum dose) is not tolerated			

Dose Modifications of Cabozantinib for Treatment-Related AEs

Event	Management	
Grade 1 AEs	Add supportive care as indicated. Continue cabozantinib treatment at the current	
	dose level if AE is manageable and tolerable.	
Grade 2 AEs which are	Continue cabozantinib treatment at the current dose level with supportive care.	
tolerable and are easily		
managed		
Grade 2 AEs which are	At the discretion of the Investigator, cabozantinib should be dose reduced or	
intolerable and cannot be	interrupted.	
adequately managed		
	Note: It is recommended that dose holds be as brief as possible.	
Grade 3 AEs (except clinically	Cabozantinib should be interrupted unless the toxicity can be easily managed with a	
non-relevant laboratory	dose reduction and optimal medical care.	
abnormalities)		
	Note: It is recommended that dose holds be as brief as possible.	
Grade 4 AEs (except clinically	Subjects should have cabozantinib interrupted immediately.	
non-relevant laboratory	Discontinue cabozantinib unless the following criteria are met:	
abnormalities)	Subject is deriving clear clinical benefit as determined by the Investigator, and	
	approved by the Principal Investigator.	
	 Toxicity can be managed with a dose reduction following recovery to Grade 1 	
	(or baseline) and optimal medical care .	
Note: The dose delay and modi	fication criteria for specific medical conditions are provided in Section 5.4.1.2.	

5.4.1.1 Cabozantinib Dose Reinstitution and Reescalation

If the subject recovers from his or her toxicities to CTCAE v.5.0 Grade \leq 1 or to the baseline value (or lower) and the toxicity was unrelated to cabozantinib, then cabozantinib may be restarted with no change in dose.

If the subject recovers from his or her toxicities to Grade \leq 1 or to the baseline value (or lower) the toxicity was deemed possibly related to cabozantinib, then cabozantinib may be restarted at a reduced dose.

Subjects who initiated treatment with cabozantinib at 40 mg and experience a possibly related AE of Grade 1 or 2 severity may be restarted with no dose change after recovery of the toxicities to \leq Grade 1 or to the baseline value (or lower) if appropriate supportive care can prevent or minimize the risk of the AE.

Subjects receiving a dose of 20 mg qod may be restarted at the same dose if deemed safe at the discretion of the investigator. Subjects unable to tolerate a dose of 20 mg qod should discontinue cabozantinib.

Re-escalation to the previous dose, (but not higher than 40 mg/day) may be allowed at the discretion of the Investigator for AEs which have resolved or recovered to Grade 1 (or baseline value) and deemed tolerable and easily managed by optimized supportive treatment. A minimum two-week interval is needed between resuming study treatment and the escalation to the next higher dose level. Dose re-escalation is not allowed for a drug-related dose reduction triggered by Grade 4 hematologic toxicities or by Grade 4 AEs affecting major organs (e.g., central nervous system, cardiac, hepatic, renal).

5.4.1.2 Guidelines for Management of Potential Adverse Events Associated with Cabozantinib Treatment

Subjects will be monitored for AEs from the time of 1st treatment through their last follow-up visit (100 days after the date of the last dose of study treatment.) Subjects will be instructed to notify their physician immediately at the onset of any AE. Seriousness, severity grade, and relationship to study treatment of AEs will be determined by the Investigator. AE severity will be graded by the Investigator in accordance with CTCAE v.5.0.

CONFIDENTIAL - Cabozantinib + Nivolimab + Ipililumab Protocol Required Elements

Management of severe or intolerable adverse reactions may require temporary dose reduction and/or interruption for cabozantinib.

The most frequent AEs experienced by \geq 20% of subjects treated with cabozantinib in descending order of frequency were diarrhea, fatigue, decreased appetite, nausea, palmar-plantar erythodysesthesia syndrome (PPES), vomiting, weight decreased, hypertension, PPES, vomiting, constipation, hypertension, dysgeusia, dysphonia, and asthenia. For a full description of the safety profile of cabozantinib, refer to the cabozantinib Investigator's Brochure.

Subjects may also experience other medically important but less frequent AEs including arterial and venous thrombotic AEs (e.g., deep vein thrombosis [DVT], pulmonary embolism, transient ischemic attack [TIA], and myocardial infarction [MI]), severe hemorrhagic events, proteinuria, wound healing complications, GI perforation, abscesses including intra-abdominal and pelvic abscess, GI and non-GI fistulae formation, osteonecrosis, and RPLS).

Adverse events associated with laboratory abnormalities experienced by ≥ 5% of subjects treated with cabozantinib in descending order of frequency were anemia, AST increased, ALT increased, hypothyroidism, hypokalemia, hypomagnesemia, thrombocytopenia, hypocalcemia, hypophosphatemia, LDH increased, lipase increased, neutropenia, ALP increased, hyponatremia, and leukopenia.

Many AEs can occur early (within the first few weeks) in the course of treatment with cabozantinib, as cabozantinib is expected to reach steady state exposure at approximately 2 weeks following first dose. Events that generally have an early onset include hypocalcemia, hypokalemia, thrombocytopenia, hypertension, PPES, abdominal pain, mucosal inflammation, constipation, diarrhea and vomiting. In addition, earlier onset for events of dehydration was observed in subjects with castrate-resistant prostate cancer (CRPC) when compared with subjects with other tumor types.

Adverse events should be managed with supportive care at the earliest signs of toxicity. Dose reductions and treatment interruptions should be considered. Dose reductions are recommended for events that, if persistent, could become serious or intolerable. Cabozantinib should be discontinued for the following AEs: visceral perforation or fistula formation, severe hemorrhage, serious arterial thromboembolic

events, nephrotic syndrome, hypertensive emergency, persistent uncontrolled hypertension despite optimal medical management, and reversible posterior leukoencephalopathy syndrome (RPLS).

A population pharmacokinetics analysis of cancer subjects with RCC, HCC, MTC, glioblastoma, and other solid tumors predicted a terminal half-life of approximately 99 h for cabozantinib when administered as repeated once-daily doses. Thus, as described above, it will take most subjects 2 to 3 weeks (5 half-lives) to reach steady state with daily dosing after initiating therapy with cabozantinib. AEs attributable to cabozantinib may be expected to occur by the time maximum plasma concentrations are reached, and therefore early intervention with dose modifications within the first 15-21 days of daily dosing may be justified.

5.4.1.2.1 Gastrointestinal Events

Gastrointestinal perforation, GI fistula, and intra-abdominal and pelvic abscess:

Prior to initiation of treatment with cabozantinib, subjects should be carefully evaluated for potential risk factors including (but not limited to) the following:

- Tumors invading GI or respiratory tracts.
- Active peptic ulcer disease, inflammatory bowel disease (e.g., ulcerative colitis, Crohn's disease),
 diverticulitis, cholecystitis or symptomatic cholangitis, or appendicitis.
- History of abdominal fistula, GI perforation, bowel obstruction, or intra-abdominal abscess.
- Ongoing visceral complications from prior radiation therapy.
- Prior GI surgery (particularly when associated with delayed or incomplete healing).

Complete healing following abdominal surgery and radiation therapy and/or resolution of intra abdominal abscess must be confirmed prior to initiating treatment with cabozantinib.

After starting cabozantinib, subjects should be monitored for early signs of GI perforation such as abdominal pain, nausea, emesis, constipation, and fever especially if known risk factors for developing GI perforation or fistula²⁰ are present.

Discontinue cabozantinib and initiate appropriate management in subjects who have been diagnosed with GI perforation or fistula.

Diarrhea: Subjects should be instructed to notify their physician immediately at the first signs of poorly formed or loose stool or an increased frequency of bowel movements. Guidelines for the evaluation and management of diarrhea are shown below.

Administration of antidiarrheal/antimotility agents is recommended at the first sign of diarrhea as initial management. Some subjects may require concomitant treatment with more than one antidiarrheal agent. When therapy with antidiarrheal agents does not control the diarrhea to tolerable levels, cabozantinib should be temporarily interrupted or dose reduced. When the diarrhea is controlled, retreatment with cabozantinib may be acceptable per Investigator decision.

In addition, general supportive measures should be implemented such as continuous oral isotonic hydration, correction of fluid and electrolyte abnormalities, small frequent meals, and stopping lactose-containing products, high-fat meals, and alcohol.

Recurrent or prolonged diarrhea can be associated with anal or perianal skin erosions which increase the risk for anal abscesses, fistulas, or proctitis. Good personal hygiene should be emphasized. Regular examinations of the perianal region should be performed whenever diarrhea has occurred during treatment with cabozantinib. Infections of the perianal region should be treated per local guidelines.

Management of Diarrhea Associated with Cabozantinib

Event	Management
Tolerable Grade 1-2 (duration < 48 h)	 Continue with study treatment and consider dose reduction. Initiate treatment with an antidiarrheal agent (e.g., loperamide 4 mg followed by 2 mg after each episode of diarrhea [maximum: 16 mg loperamide per day]). Dietary modifications (e.g., small lactose-free meals, bananas and rice). Intake of isotonic fluids (1-1.5 L/day). Re-assess after 24 hours: Diarrhea resolving to baseline bowel habits: gradually add solid foods and discontinue or decrease antidiarrheal treatment after 12 h diarrhea-free interval. Diarrhea not resolving: Continue/resume antidiarrheal treatment.
Intolerable Grade 2, Grade 2 > 48 h, or ≥ Grade 3	 Interrupt study treatment. Ask subject to attend clinic. Rule out infection (e.g., stool sample for culture). Administer antibiotics as needed (e.g., if fever or Grade 3-4 neutropenia persists > 24 h). Administer fluids (1-1.5 L/day orally or IV, as appropriate) for hydration or to correct electrolyte abnormalities. For Grade 3-4 or complicated lower grade diarrhea consider hospitalization and IV hydration. Re-assess after 24 h. Diarrhea resolving to baseline bowel habits or Grade ≤ 1: consider restarting study treatment at reduced dose. Diarrhea not resolving: Start and or continue antidiarrheal treatment (e.g., loperamide 4 mg followed by 2 mg after each episode of diarrhea [maximum: 16 mg loperamide per day]). Consider starting second line antidiarrheal or referral to gastroenterologist.

Nausea and vomiting: Antiemetic agents are recommended as clinically appropriate for treatment or prophylaxis of nausea and vomiting, along with supportive care. Dehydration and electrolyte abnormalities may be associated with vomiting and monitoring for and correction of fluid and electrolyte disturbances should be implemented. Antiemetic medications should be assessed for potential drug interactions (refer to Section 6 for further details).

5.4.1.2.2 Hepatic Events

See section 5.4.3 for guidance regarding both cabozantinib and IO agent.

5.4.1.2.3 Non-Gastrointestinal Fistula

Radiation therapy (in certain areas of the body) has been identified as a possible predisposing risk factor for fistula formation in subjects undergoing treatment with cabozantinib.

Subjects with any clinically relevant ongoing complications from prior radiation therapy (e.g., radiation esophagitis or other inflammation of the viscera) should not be treated with cabozantinib until these complications have resolved.

Radiation therapy to the thoracic cavity (including mediastinum) should be avoided within 4 weeks of starting treatment with cabozantinib (excluding local radiation for bone metastases). Fistula should be ruled out as appropriate in cases of onset of severe mucositis or difficulty swallowing after start of therapy. Discontinue cabozantinib and initiate appropriate management in subjects who have been diagnosed with a non GI fistula.

5.4.1.2.4 Hemorrhage

Hemorrhagic events, including serious and sometimes fatal events, have been reported with cabozantinib. Subjects should be evaluated for potential bleeding risk factors prior to initiating cabozantinib treatment and should be monitored for bleeding events with serial complete blood counts and physical examination while on study. Risk factors for hemorrhagic events may include (but may not be limited to) the following:

- Tumor of the lung with cavitary lesions or tumor lesions which invade or encase major blood
 vessels. NSCLC with squamous cell differentiation is known for significant lung cavitations and
 centrally located tumors that may invade major blood vessels. Thus, the anatomic location and
 characteristics of tumor as well as the medical history should be carefully reviewed in the
 selection of subjects for treatment with cabozantinib.
- Recent or concurrent radiation to the thoracic cavity.
- Active peptic ulcer disease, inflammatory GI diseases including Crohn's disease and ulcerative colitis.
- Underlying medical conditions which affect normal hemostasis (e.g., deficiencies in clotting factors and/or platelet function, or thrombocytopenia).
- Concomitant medication with anticoagulants or other drugs which affect normal hemostasis.

 CONFIDENTIAL Cabozantinib + Nivolimab + Ipililumab Protocol Required Elements

• History of clinically significant hemoptysis, hematemesis, or hematuria.

The risk of hemorrhage in cabozantinib-treated subjects with brain metastases has not been thoroughly analyzed. Though the incidence of CNS hemorrhage events in a study of subjects with glioblastoma was higher than observed in general population of subjects with cancer treated with cabozantinib, it is not clear how the risk of hemorrhage in glioblastoma translates to a risk of hemorrhage for subjects with brain metastases. Currently, brain metastases of carcinomas are not contraindications to the use of cabozantinib, but subjects with brain metastases should be monitored with a high index of suspicion if symptoms that could be due to a CNS hemorrhage occur.

Complete healing from radiation-induced side effects should have occurred before initiating cabozantinib treatment, and cabozantinib should be discontinued in subjects with serious and life-threatening bleeding events or recent hemoptysis (≥ 2.5 mL of red blood).

5.4.1.2.5 Vascular Disorders

Thromboembolic Events

Thromboembolic events are frequent in cancer subjects due to procoagulant changes induced by the malignancy or anticancer therapy. DVT and pulmonary embolism have been observed in clinical studies with cabozantinib, including fatal events. Subjects who develop a pulmonary embolism and/or DVT should have study treatment interrupted until therapeutic anticoagulation is established. Treatment with cabozantinib may be resumed in subjects with pulmonary embolism or DVT if it is determined that the event is uncomplicated and that the subject is deriving clinical benefit from cabozantinib treatment and that anticoagulation does not place them at a significant risk that outweighs the benefit of resuming treatment per discretion of the Investigator and according to individual protocols. Therapeutic doses of LMWH or the direct factor Xa oral inhibitors rivaroxaban, edoxaban, or apixaban are allowed for management of thrombotic events. Other oral anticoagulants including coumarin agents (e.g., warfarin), direct thrombin inhibitors (e.g., dabigatran), direct factor Xa inhibitor betrixaban, platelet inhibitors (e.g., clopidogrel), and chronic use of aspirin above low dose levels for cardioprotection per local

applicable guidelines are not allowed, until 4 weeks after cabozantinib has been permanently discontinued. See Section 6.2 for additional restrictions on anticoagulation therapy.

Arterial thrombotic events (e.g., TIA, MI) have been observed in studies with cabozantinib. Subjects should be evaluated for pre-existing risk factors for arterial thrombotic events such as diabetes mellitus, hyperlipidemia, hypertension, coronary artery disease, history of tobacco use, and cardiac and/or thromboembolic events that occurred prior to initiation of study treatment. Further treatment with cabozantinib should be discontinued in subjects who develop an acute MI, cerebral infarction, or any other clinically significant arterial thromboembolic complication.

Hypertension

The below table provides treatment guidelines for hypertension deemed related to cabozantinib. Subjects with known hypertension should be optimally managed prior to entry into clinical trials with cabozantinib according to entry criteria of specific protocols. Blood pressure should be monitored in a constant position visit to visit, either sitting or supine in a relaxed setting. Decisions to reduce or interrupt the dose of study treatment must be based on BP readings taken by a medical professional and must be confirmed with a second measurement at least 5 minutes following the first measurement.

Cabozantinib should be discontinued in subjects with hypertensive emergency.

Management of Hypertension Associated with Cabozantinib

Event	Management	
Subjects NOT receiving optimized anti-hypertensive therapy		
> 140 mm Hg (systolic) ^a and < 160 mm Hg	Optimize antihypertensive medications by adding new or additional antihypertensive medications and/or increase dose of existing	
OR	medications.Reduce cabozantinib treatment by one dose level if optimal	
> 90 mm Hg (diastolic) and < 110 mm Hg	antihypertensive therapy (usually to include 3 agents) does not result in BP <140 mm Hg systolic or <90 mm Hg diastolic.	
	If subject is symptomatic interrupt cabozantinib treatment	
≥ 160 mm Hg (systolic)	Reduce cabozantinib by one dose level ^b or interrupt cabozantinib	
OR	treatment per Investigator discretion.Add new or additional anti-hypertensive medications and/or increase	
≥ 110 mm Hg (diastolic)	dose of existing medications and monitor subject closely for hypotension. If optimized antihypertensive therapy (usually to include 3 agents) does not result in BP < 140 mm Hg systolic or < 90 mm Hg	
	diastolic, cabozantinib treatment should be dose reduced further or interrupted.	
	Cabozantinib treatment should be dose interrupted if upper limits of systolic BP (≥ 160 mm Hg) are sustained and not adequately	
	manageable or if systolic BP is > 180 mm Hg or diastolic BP > 110 mm Hg, or if subject is symptomatic.	
	Re-start cabozantinib treatment at the most tolerable dose and	
	re-escalate only if BP falls to and is sustained at < 140 mm Hg systolic and < 90 mm Hg diastolic.	
Hypertensive emergency ^c	Discontinue cabozantinib treatment.	

^a Permitted dose levels are defined by individual protocols.

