3.2 Exclusion Criteria

- 1. Prior therapy:
 - a)
 - b) Prior therapy with a VEGF(R) inhibitor alone or in combination with immune checkpoint inhibitor(s).
 - c) Prior therapy with an anti-CTLA-4 antibody
- 2. Participants with active, known, or suspected autoimmune disease. Participants with type I diabetes mellitus, residual hypothyroidism due to autoimmune thyroiditis only requiring hormone replacement, skin disorders (such as vitiligo, psoriasis, or alopecia) not requiring systemic treatment are permitted to enroll.
- 3. Participants with a condition requiring systemic treatment with either corticosteroids (> 10 mg daily prednisone or equivalent) or other immunosuppressive medications within 14 days of study drug administration. Inhaled or topical steroids are permitted in the absence of active autoimmune disease.
- 4. History of allergy or hypersensitivity to any monoclonal antibody
- 5. Previous or concurrent malignancy within 3 years of study entry, with the following exceptions:
 - a) adequately treated basal or squamous cell skin cancer, superficial bladder cancer, prostate intraepithelial neoplasm, carcinoma in-situ of the cervix, or other noninvasive or indolent malignancy; OR
 - b) other solid tumors treated curatively in which the expected rate of recurrence within 5 years is < 5%.

CONFIDENTIAL - Cabozantinib + Nivolimab + Ipililumab Protocol Required Elements

- 6. Impaired cardiovascular function or clinically significant cardiovascular diseases, including any of the following:
 - History of acute coronary syndromes (including myocardial infarction, unstable angina, coronary artery bypass grafting, coronary angioplasty, or stenting) <6 months prior to screening,
 - Symptomatic congestive heart failure (i.e. Grade 2 or higher), history or current evidence of clinically significant cardiac arrhythmia and/or conduction abnormality <6 months prior to screening. Exceptions include asymptomatic/well-controlled atrial fibrillation/flutter or paroxysmal supraventricular tachycardia;
 - Uncontrolled hypertension defined as persistent elevation of systolic blood pressure ≥ 140 mmHg or diastolic blood pressure ≥ 90 mmHg, despite medical therapy
- 7. History of thromboembolic or cerebrovascular events ≤ 6 months prior to the first dose of study treatment. Examples include transient ischemic attacks, cerebrovascular accidents, hemodynamically significant (i.e., massive or sub-massive) deep vein thrombosis or pulmonary emboli.

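### Cabozantinib hypertension table: the target that decides dose reduction is ambiguous when only one blood-pressure component stays raised, and it does not match the entry, re-escalation or exclusion rules

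*Combined protocol and SAP*

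**What the plan says.** The table on managing cabozantinib-related hypertension (section 5.4.1.2.5) has two non-emergency rows.

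- **Lower row, entry:** systolic "> 140 mm Hg (systolic) ^a and < 160 mm Hg", or diastolic above 90 and below 110. Either is enough.
- **Lower row, dose action:** reduce one level if optimal "antihypertensive therapy (usually to include 3 agents) does not result in BP <140 mm Hg systolic or <90 mm Hg diastolic". The only other dose instruction in the row is to interrupt if the subject has symptoms.
- **Upper row, entry:** systolic at or above 160, or diastolic at or above 110. The action on entry is "Reduce cabozantinib by one dose level ^b or interrupt cabozantinib" treatment, at the investigator's discretion.
- **Upper row, follow-on:** the lower row's control test is repeated, with the two limits again joined by *or*. Failure leads to a further reduction or an interruption.
- **Upper row, separate interruption line:** it applies if upper limits of "systolic BP (≥ 160 mm Hg) are sustained and not adequately" controllable, and it continues "manageable or if systolic BP is > 180 mm Hg or diastolic BP > 110 mm Hg, or if subject is symptomatic".
- **Upper row, restart:** "re-escalate only if BP falls to and is sustained at < 140 mm Hg systolic and < 90 mm Hg diastolic".

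Three other places bear on this. Exclusion criterion 6 (section 3.2) defines uncontrolled hypertension as "persistent elevation of systolic blood pressure ≥ 140 mmHg or diastolic blood pressure ≥ 90 mmHg, despite medical therapy". Section 5.4.1 lets the investigator change the dose at any time. Section 5.4.1.2 lists hypertension that stays uncontrolled under optimal treatment among the reasons to discontinue cabozantinib, but does not define uncontrolled.

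**The concern.** The same two limits, 140 and 90, are joined by *and* in the re-escalation line and by *or* in the two dose-action lines. Because the dose-action lines are negated, the connective matters: failing an *or* target means that both components are still high. A subject who enters the lower row on one component alone already meets that target before any antihypertensive is adjusted. The row's only dose action for asymptomatic subjects would then never apply to that subject while the other component stays under its limit.

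What is at stake is a stated safety rule. Two investigators acting in good faith could make opposite dose decisions from the same measurement. Section 5.4.1.2 lists hypertension among the events seen in at least 20% of cabozantinib-treated subjects and among those that tend to start early, so the table will be used. If the trial expands by one or two sites, as sections 2 and 8 foresee, more people will have to interpret it. Uneven dose decisions would also add noise to the exposure and safety data of a 25-subject trial.

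**Working it through.** The plan states no figure to reproduce, so this is a check of the table's logic.

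**Definitions.** Let A = systolic <140 and B = diastolic <90.

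- Literal interpretation of the dose-action line: act if not(A or B) = (not A) and (not B), that is, both raised.
- Either-component interpretation: act if not(A and B) = (not A) or (not B), that is, at least one raised.
- Re-escalation line: A and B.
- Exclusion 6: uncontrolled if systolic ≥140 or diastolic ≥90, which is (not A) or (not B).

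The two interpretations differ exactly when one of A and B holds and the other does not.

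**Applied to asymptomatic subjects on optimized therapy:**

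| BP | Row | Control line acts: literal | Control line acts: either-component | Re-escalation test met | Uncontrolled by exclusion 6, if persistent | Triggers independent of the control line |
|---|---|---|---|---|---|---|
| 158/84 | lower | no | yes | no | yes | none |
| 130/95 | lower | no | yes | no | yes | none |
| 150/95 | lower | yes | yes | no | yes | none |
| 165/80 | upper | no | yes | no | yes | row entry; interruption if sustained and not manageable |
| 185/80 | upper | no | yes | no | yes | row entry; sustained line; >180 |
| 130/112 | upper | no | yes | no | yes | row entry; >110 |
| 135/85 | none | no | no | yes | no | none |

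**What is lost under the literal interpretation:**

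1. In the lower row, the one-level reduction for an asymptomatic subject with systolic >140 to <160 and diastolic <90, or diastolic >90 to <110 and systolic <140. Isolated diastolic elevation is affected as much as isolated systolic elevation.
2. In the upper row, the follow-on step when one component is under its limit and no other trigger applies. For example, a subject enters at 165/80, the dose is reduced on entry, and optimized therapy brings the pressure to 150/80. The literal target is met through 80 <90, so no further step is called for. The either-component interpretation calls for one.

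**Three outcomes for a persistent 158/84.** The literal table gives no dose action. The either-component interpretation gives a one-level reduction. Section 5.4.1.2, with uncontrolled taken from exclusion 6, gives discontinuation.

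**Rough scale.** If the 20% floor for hypertension carried over to this trial (an assumption), at least 0.20 × 25 = 5 subjects would have hypertension, or about 0.20 × 41 = 8 after expansion. The documents do not say how many of these would have only one component raised, so the number affected lies anywhere from none to all of them.

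**The case against.** The strongest reply is linguistic. In ordinary prose, not achieving one limit or the other can mean missing either one. That sense fits the entry rule and exclusion 6, and it avoids a target that some subjects meet on arrival. It may well be what the authors meant. What remains is that the same table writes *and* where it wants both components below the limit, so a careful reader could take *or* as deliberate. The documents do not settle it.

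Second, a stricter condition for raising a dose than for holding it is not a contradiction, and an eligibility criterion serves a different purpose from a management rule. Both points are fair. Neither comparison alone would prove an error. The comparison with the row-entry rule is the more telling one.

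Third, the table offers guidance, and section 5.4.1 permits dose changes at any time. That is true. However, the general dose-modification table in section 5.4.1 sends readers to section 5.4.1.2 for condition-specific criteria, so the hypertension table is where a stated rule would be looked up.

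A reader might go further and infer that isolated systolic hypertension never triggers a dose action, or that such a subject could go unaddressed for the full 24 months of treatment. The documents do not support that. Systolic pressure at or above 160 calls for reduction or interruption on row entry. Sustained pressure at or above 160 that cannot be managed, systolic above 180, and symptoms each call for interruption. None of these uses the *or* line. Discretionary changes are open throughout, and the discontinuation entry in section 5.4.1.2 can reach persistent cases. The last of these is only a partial safeguard, because its key word is undefined.

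**Conclusion.** The point holds as an unresolved ambiguity in a stated safety rule. It is not a demonstrated absence of protection. It affects two dose-action lines and the subjects for whom exactly one component is at or above its limit and no independent trigger applies. For them the documents support no action, a one-level reduction or discontinuation, depending on the place consulted and the interpretation taken.

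This rests on the table text as extracted and on the absence of a definition of controlled pressure elsewhere in the protocol. It does not depend on how often the pattern occurs, which the documents do not allow one to estimate. Sample size, endpoints and the planned analyses are untouched. The ambiguity should be corrected because it bears directly on how subjects are managed and costs little to remove. Which rule is clinically right is outside this review.

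**What to change.** State explicitly, once, whether one or both components must be below the limit for blood pressure to count as controlled. Then reconcile these places with that statement:

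- the dose-action line in the lower row and the follow-on line in the upper row of the section 5.4.1.2.5 table;
- the row-entry and re-escalation lines of the same table;
- exclusion criterion 6 in section 3.2;
- the discontinuation entry for uncontrolled hypertension in section 5.4.1.2, which should refer to the same definition.

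If the sponsor intends different thresholds for reducing and for raising the dose, the table should say so. The rule itself is the sponsor's decision.

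The cost is a few words in the table and a cross-reference, submitted through the amendment process in section 11. No assessment, visit or analysis changes.
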